Statistical Analyses	
Cross-sectional analyses will include a comparison of FM patients with HC with respect to GABA, Glx and other neuroimaging biomarkers (t-tests, linear regression);
 
Longitudinal analysis will study treatment effects on within-patient change in neuroimaging biomarkers and changes in clinical pain (t-tests, linear regression with change as a response, linear mixed model with biomarker as a response); treatment and biomarker predictive effects at baseline on clinically relevant 50% reduction of pain as a binary response (logistic regression); the effects of treatment and biomarker baseline measurements on within-patient change in DMN-insula connectivity; biomarker mediation analysis for the treatment effect.
 
In order to screen neuroimaging biomarkers that respond to treatment (show reduced DMN-insula connectivity), interim testing for futility will be performed.
 
Reasons for missingness will be analyzed using multinomial logistic regression with treatment as one of the covariates. The results of formal missing data imputation by predictive-matching algorithms will be compared to the results of missing data exclusion in a sensitivity analysis.

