This aim evaluates a *mechanistic* value of the neuroimaging biomarkers by studying their response to treatment and correlation between the change in biomarker measurements and changes in pain induced by treatments, and biomarker mediation effects.

Hypothesis 1: EA, which involves greater somatosensory afference, will more readily reduce resting insula connectivity to SMN and DMN compared to ML. The change in pain will correlate with change in insula connectivity for EA, but not ML. Insula connectivity will represent a mediator for the treatment effect.

Treatment effects on connectivity

We will perform dual-regression ICA with group level estimates for baseline and post-treatment fcMRI data (DMN and SMN) entered into a linear mixed model with factors STIM (levels EA, ML) and TIME (levels baseline and post-therapy). Time by treatment interaction effect will be of main interest in the analysis. If a significant main effect or interaction is found, we will perform post-hoc difference map analyses, to evaluate which group produced the greatest change in resting connectivity.

Power analysis for fcMRI is based on data from the preliminary study on intrinsic connectivity and its short-term response to acupuncture. From preliminary data on 15 subjects, we estimate the SD of the number of voxels activated before and after acupuncture in the default mode independent component to be 2860 and 4559, respectively. The covariance between these before and after counts is 3388878. This implies the standard deviation of the within-subject change in connectivity of $\sqrt{2860^2+4559^2-2*3388878}=4710$. Based on the same data, we find the before and after means to be 7078 and 9844, respectively. Then, a two-sided paired t-test for the presence of change will have the effect size of 0.6 and the power of 95% with 40 patients in the EA group.

Based the similar mean connectivity difference of around 3000 between ML and EA, and the same SD of 4710 we will have 80% power to detect the difference between treatments with respect to the mean within-patient change in connectivity.

Correlation with pain

A linear mixed model will be used to regress BPI pain measurements on the neuro-imaging biomarkers. Correlation between clinical pain and biomarkers is the primary target.

We hypothesize a correlation coefficient of at least 0.5 between pain and connectivity z score in the EA arm. This will give us 94% power to detect the correlation.

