Interim analysis. After 50% of the subjects have been enrolled and evaluated, we will determine if fcMRI outcome metrics are sensitive enough to continue using for the biomarker for the duration of the study. Screening of biomarkers (brain regions) will be done by computing a post-hoc power based on 20 patients per arm. Biomarkers showing post-hoc power lower than 20% will not be pursued further. This decision corresponds to dropping biomarkers showing correlation coefficients less than 0.18 in the interim analysis.

Mediation Analysis

In the linear mixed model regressing BPI pain score on treatment and time, the effect of treatment on pain is expressed as a regression coefficient for time specific to treatment group (or a treatment by time interaction). Mediation effect will be measured as the proportion of treatment effect explained by the biomarker (PTE) representing a relative change in the regression coefficient when biomarker is included in the model (relative to the coefficient before biomarker inclusion into the model). Standard error for the PTE will be estimated by bootstrap, and a two-sided 95% interval for the effect will be constructed. Wald test with the statistic of the form (change in regression coefficient)/(bootstrap SE) will be used to test for the mediation effect. Similar analyses will be done using a logistic regression model with clinically relevant reduction in pain (defined as 50% and 30%) as a response.

Power. We use Sobel's test based on linear regression to compute power. Power analysis targets biomarkers with the mediation effect of PTE=0.5. We assume that the regression coefficient in the model for the treatment effect on connectivity is 3000; treatment effect beta in the model of change in pain excluding the biomarker is 2; standard deviation of the randomized treatment variable 0.5; standard deviation of the change in connectivity over time 4500 voxels; squared the correlation between the treatment variable and the change in connectivity $3.7e-05$; standard deviation of errors in the full model regressing change in pain on both treatment and the biomarker 1.5. These assumptions are consistent with the ones made previously in the power calculations related to different lags of the mediation analysis, with our preliminary data, and with the acupuncture effects on pain reported in the literature. Under these assumptions we will have the power of 81% to detect the mediation effect by Sobel's test.[114]

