Hypothesis 2 : EA will more readily reduce Glx and increase GABA in the insula as compared to ML, which will not reduce Glx and GABA. The change in pain will correlate with change in insula GABA and Glx for EA but not ML. Glx and GABA will represent mediators for the treatment effect on change in pain.

Similar to above, linear mixed models and paired t-test analyses will evaluate, separately, Glx and GABA concentration levels taken from baseline and post-therapy H-¹MRS scans.

A reduction in the Glx of about 1.5 arbitrary institutional units (AIU) with a standard deviation not exceeding 0.6 is expected in the EA group. At the same time in the ML group a much smaller effect is expected (around 1 AIU, same standard deviation). This ensures 95% power when using a two –sided test. A similar analysis for differences in the change in GABA of 0.3 vs. 0.1 mmol/kg with a standard deviation of 0.25 gives 94% power to detect a difference.

Correlation between Glx/GABA and clinical pain (BPI) will be analyzed similar to the fcMRI biomarkers. The study has 94% power to detect correlations of 0.5 and higher.

Similar to fcMRI biomarkers, if Glx or GABA show less than 20% post-hoc power after half of the patients have been measured (correlation less than 0.18), their longitudinal measurements will be discontinued for the remaining patients.

Mediation Analysis is similar to the one proposed for connectivity.

Hypothesis 3: EA will more readily reduce pain-evoked fMRI activation in the insula as compared to ML, which will not reduce pain-evoked fMRI activation. The change in pain will correlate with change in insula response to evoked pain for EA but not ML. Insula response to evoked pain will represent a mediator for the treatment effect on change in pain.

Parameter estimates from evoked pain block-design fMRI scans will be used in a linear mixed model and post-hoc paired t-tests, similar to the approach described above.

Changes in connectivity z-score for a typical connectivity biomarker are expected to follow a different slope in EA vs. ML patients in response to pressure pain. Assuming the slope of 1.3 vs. 0.5 with the standard deviation of the pain score of approximately 1 and standard deviation of the connectivity z score at a given level of pressure pain of around 1. This ensures we will have over 94% power to detect a difference in connectivity by pressure pain slope responses with 40 patients per treatment group.

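### The interim rule can stop Glx and GABA follow-up on a correlation the plan does not define, and the stated EA-versus-ML powers make no allowance for that stop

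*Combined protocol and SAP*

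**What the plan says.** The rule is set out under Section 11.2 (Aim 2), Hypothesis 1, in the interim analysis paragraph, and applies once half the subjects have been enrolled and evaluated. "Screening of biomarkers (brain regions) will be done by computing a post-hoc power based on 20 patients per arm". Then: "Biomarkers showing post-hoc power lower than 20% will not be pursued further". The threshold is restated as a correlation: "This decision corresponds to dropping biomarkers showing correlation coefficients less than 0.18 in the interim analysis". The text just before it concerns BPI pain and says "Correlation between clinical pain and biomarkers is the primary target", with a hypothesised correlation of at least 0.5 in the EA arm.

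Hypothesis 2 of the same section carries the 20% and 0.18 thresholds over to Glx and GABA, directly after a sentence on their correlation with BPI pain, and gives a harder consequence: "their longitudinal measurements will be discontinued for the remaining patients".

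Hypothesis 2 also has a treatment comparison: "EA will more readily reduce Glx and increase GABA in the insula as compared to ML". It is powered at 95% for Glx (change of 1.5 versus 1 AIU, SD 0.6). For GABA (0.3 versus 0.1 mmol/kg), the change "with a standard deviation of 0.25 gives 94% power to detect a difference".

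The Synopsis (Section 2) gives the purpose of the interim look: "In order to screen neuroimaging biomarkers that respond to treatment (show reduced DMN-insula connectivity), interim testing for futility will be performed". Section 11.3 ranks mechanistic results above predictive ones, but does not say what happens when treatment response and pain correlation disagree.

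**The concern.** Two things look wrong. First, the rule cannot be carried out as written. It does not name the two variables, whether they are levels or changes, the arm or arms, or the sign.

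Second, the consequence for Glx and GABA reaches beyond the quantity screened. Section 11.2 gives mechanistic value three parts: response to treatment, correlation of change with pain, and mediation. One interim correlation can end data collection for all three, and follow-up spectra that were not acquired cannot be recovered. The EA-versus-ML powers are quoted as if this could not happen.

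**Working it through.** **Inputs.** 40 EA and 40 ML patients (Synopsis). Changes, SDs and stated powers from Section 11.2, Hypothesis 2. Interim at 20 per arm, cut-off 0.18, correlation 0.5 in EA, pain effect of 2 points and residual pain SD of 1.5 from Section 11.2, Hypothesis 1. Two-sided alpha of 0.05 is stated for Aim 1 and assumed here for Aim 2.

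**Step 1: the plan's own powers.** Two-sample t-test on change, with d = difference/SD, noncentrality d × √(n/2) and 2n − 2 degrees of freedom.

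- Glx: d = 0.5/0.6 = 0.833. At 40 per arm, 0.833 × √20 = 3.73, power 95.7%. At 20 per arm, 0.833 × √10 = 2.64, power 72.8%.
- GABA: d = 0.2/0.25 = 0.80. At 40 per arm, 0.80 × √20 = 3.58, power 94.2%. At 20 per arm, 0.80 × √10 = 2.53, power 69.3%.

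The stated 95% and 94% are therefore full-sample figures. If 25 per arm already have follow-up when measurement stops, power is about 82% and 79%.

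**Step 2: what 0.18 can mean.**

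- Correlation with pain, Fisher z: power = Φ(z√(n−3) − 1.96) + Φ(−z√(n−3) − 1.96), with z = atanh(0.18) = 0.182. At n = 40 (both arms pooled), 0.182 × √37 = 1.107 and power is 19.8%. At n = 20 (EA only), 0.182 × √17 = 0.750 and power is 11.7%.
- Correlation of biomarker change with treatment arm: d = 2r/√(1 − r²) = 0.36/√(1 − 0.0324) = 0.366. A two-sample t-test at 20 per arm has 20.4% power.

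A pooled pain correlation and a treatment correlation both reproduce the 20%, so the arithmetic does not settle which is meant. An EA-only pain correlation does not reproduce it at the interim size.

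**Step 3: power averaged over stopping.** Simulation with 60,000 to 100,000 runs per case: normal changes with unit SD within arm, the planned Glx or GABA effect, the correlation shown in EA and zero in ML. The stop applies if |r| < 0.18 at 20 per arm; the final test then uses 20 per arm, otherwise 40. The 2-point pain effect is scaled by an SD of 1.5 to 1.5/√(1 − 0.5²) = 1.73, that is 1.33 to 1.155 SD.

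| Screen | True correlation in EA | Chance of stop | Average power, Glx / GABA |
|---|---|---|---|
| No stop | any | 0 | 95.7% / 94.2% |
| Pain, EA only | 0.5 | 6% | 95% / 93% |
| Pain, pooled, 2-point effect | 0.5 | 6–8% | 92–93% / 91% |
| Pain, pooled, no pain effect | 0.5 | 36% | 88% / 86% |
| Pain, EA only | 0.3 | 27% | 90% / 88% |
| Pain, EA only | 0 | 55% | 83% / 81% |
| Pain, pooled, no pain effect | 0 | 73% | 79% / 76% |
| Treatment contrast | not used | 7% / 8% | 91% / 89% |

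Losses in percentage points, from unrounded powers:

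- Plan's assumptions, pain screen: from 95.7 − 94.7 = 1.0 to 94.2 − 90.6 = 3.6.
- Treatment screen: 95.7 − 91.1 = 4.6 and 94.2 − 88.9 = 5.3.
- Zero correlation with pain: from 95.7 − 83.2 = 12.5 to 94.2 − 75.9 = 18.3.

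**The case against.** The strongest defence is that the pain reading is only inferred. The interim size is given per arm, as for a two-arm contrast, and a treatment correlation of 0.18 gives 20.4% power at that size. The Synopsis also speaks of response to treatment. On that reading the Synopsis and Section 11.2 agree. This stands: a reader might infer that they contradict each other, but the documents do not establish it, and the Synopsis sentence names only DMN-insula connectivity, not Glx or GABA. What remains is that the statistic is not defined, and the power statement omits the stop on either reading.

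Three further points stand. The average loss is small if the plan's hypotheses hold. The 73% and 69% are floor figures, because patients already under way may still have follow-up. And if pain correlation is the target, stopping a marker with zero correlation is what a futility rule is meant to do, so that stop is not an error in itself; it still takes data from the separate treatment comparison.

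Two stronger readings are tempting but unsupported. One is that GABA is almost certain to be dropped, because it should rise as pain falls and a negative correlation is below 0.18. That requires the 0.18 restatement to be read as signed and to override the operative criterion, which is post-hoc power. At r = −0.5 two-sided power is 92% (n = 40) or 62% (n = 20), so GABA would be kept. The other is that connectivity power also collapses. Section 11.2 says only that such markers are not pursued, not that scanning stops; follow-up resting images stay in the Section 3.1 schedule and are shared under Section 12.3.2.

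**Conclusion.** The point holds in this form: Glx and GABA follow-up can be stopped at half enrolment on an undefined correlation, and the stated EA-versus-ML powers are valid only without that stop. Conditional on a stop at 20 per arm, they fall from 95.7% and 94.2% to about 73% and 69%.

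Averaged over stopping, the cost is modest if the plan is right: about 1 to 4 points for a pain screen on |r| with a correlation of 0.5 in EA and the 2-point pain effect, and about 5 points for a treatment screen. It is about 8 points if arms are pooled and do not differ in pain, and about 13 to 18 only if a metabolite responds to EA but has no correlation with pain. These figures assume normal data, alpha of 0.05, zero correlation in ML and no dropout. The issue is lost power and lost mediation data. It should be fixed, but it does not undermine the design.

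**What to change.** Keep acquiring Glx and GABA at the already scheduled Visit 12 MRI in all fibromyalgia patients, and make the interim screen a non-binding reporting flag. The stated powers then stand as written. This needs a wording change and no extra patients or visits. The cost is the scan time the stop would have saved. With 2 minutes of PRESS and 256 × 1.8/60 = 7.7 minutes of MEGA-PRESS per voxel, two voxels take 2 × 2 + 2 × 7.7 = 19.4 minutes per patient, or about 13 scanner hours over 40 patients. This lies within the two-hour session in Section 9.3. It assumes MEGA-PRESS in both voxels, which Section 9.3.2 does not state, and leaves out water reference and shimming. Manual spectral post-processing is additional.

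If the stop is kept:

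- Make the Synopsis and both Section 11.2 statements refer to one named statistic, giving the variables, change or level, arm(s) and n.
- Apply 0.18 to the absolute value, because GABA is expected to rise as pain falls.
- Restate the Glx and GABA powers with the stop included.

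Moving the stop to the treatment contrast is not a remedy: it gives average power of 91% and 89%, below the pain screen under the plan's own assumptions.

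### The linear mediation model leaves open whether the treatment effect on pain is a within-arm time coefficient or the treatment-by-time interaction; only the interaction is an EA–ML effect

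*Combined protocol and SAP*

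**What the plan says.** Section 11.2, Hypothesis 1, Mediation Analysis, regresses BPI pain on treatment and time in a linear mixed model. There, "the effect of treatment on pain is expressed as a regression coefficient for time specific to treatment group (or a treatment by time interaction"). The PTE is described as "representing a relative change in the regression coefficient when biomarker is included in the model", and "Wald test with the statistic of the form (change in regression coefficient)/(bootstrap SE) will be used to test for the mediation effect". No sentence says which of the two coefficients enters the PTE and the test. Hypotheses 2 and 3 take over the same method for Glx, GABA and evoked-pain activation.

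Elsewhere the section leans towards a between-arm effect. For connectivity itself, "Time by treatment interaction effect will be of main interest in the analysis". The mediation power paragraph takes a treatment effect on connectivity of 3000 and describes a randomised treatment variable with SD 0.5.

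**The concern.** With two arms and two visits, the two alternatives are different quantities. An arm-specific time coefficient is the mean before-after change in that arm. It contains everything that moves pain over the treatment weeks, including placebo response and natural course. The interaction is the difference between the two changes, and it alone is protected by randomisation.

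The choice carries through to mediation. Adding the biomarker to the model removes from an arm's time coefficient whatever goes with that arm's mean biomarker change, whether or not the other arm changed just as much. The trial asks whether somatosensory afference, which is what separates EA from mock laser, drives the analgesia. A within-arm PTE cannot answer that.

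Shared change is not far-fetched. The Glx power assumption in Section 11.2 has EA falling by about 1.5 AIU, while "in the ML group a much smaller effect is expected (around 1 AIU, same standard deviation"). Section 6.2.4 reports earlier data in which DMN–insula connectivity fell after both manual acupuncture and a sham with somatosensation. That sham is not mock laser, but it shows that such a fall need not be specific to verum treatment. Because the two options can give opposite answers, leaving the choice open until results are known also invites selective reporting.

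**Working it through.** **1. Which effect was powered?** Inputs, all from the mediation power paragraph: "Power analysis targets biomarkers with the mediation effect of PTE=0.5"; "regression coefficient in the model for the treatment effect on connectivity is 3000" (a = 3000); total effect on change in pain 2; treatment SD 0.5; SD of change in connectivity 4500; residual SD 1.5; squared correlation ρ² = 3.7e-05. Then b = 0.5 × 2 / 3000 = 1/3000 per voxel.

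Sobel: z = ab / √(a²Var(b) + b²Var(a)), with Var(b) = 1.5² / (n·4500²·(1−ρ²)) and Var(a) = 4500²·(1−ρ²) / (n·0.5²).

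- n = 80: a²Var(b) = 0.0125 and b²Var(a) = 0.1125, so z = 1/√0.125 = 2.83 and two-sided 5% power is 80.7%. This reproduces the stated 81%.
- n = 40 in the same formula: z = 2.00, power 51.6%.
- A one-sample version in the EA arm alone (mean change 3000, Var(a) = 4500²/40, Var(b) = 1.5²/(40·4500²)): z = 1/√(0.05625 + 0.025) = 3.51, power 93.9%.

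Only the between-arm effect in 80 patients gives 81%. (The stated ρ² equals 3000·0.5²/4500². The plan's inputs give (3000·0.5/4500)² = 0.111, and power is then 80% to 84% depending on the variance form, so the conclusion is unaffected.)

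**2. What each option tests.** In change-score form, ΔY = α_EA·T + α_ML·(1−T) + β·ΔM + error, where T is 1 for EA. Adding ΔM to the model changes

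- the EA time coefficient by β × mean ΔM in EA;
- the interaction by β × (mean ΔM in EA − mean ΔM in ML).

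With equal biomarker change in both arms the second is zero on average, and the first is not.

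**3. Simulation of the plan's Wald test.** 40 per arm, 2000 trials, 400 bootstrap draws stratified by arm, biomarker SD 4500, error SD 1.5, reject if |z| > 1.96. The two-sided 5% level is inferred from the plan's statement that "a two-sided 95% interval for the effect will be constructed". The split of the pain effect into direct and mediated parts is assumed.

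| Biomarker fall (EA / ML), relation to pain | Direct EA–ML effect on pain | EA time coefficient rejects | Interaction rejects |
|---|---|---|---|
| 3000 / 3000, b = 1/3000 | 2 | 98.4% | 5.6% |
| 3000 / 3000, b = 1/3000 | none | 98.8% | 4.3% |
| 1500 / 1500, b = 1/3000 | 2 | 53.4% | 4.6% |
| 0 / 0, b = 1/3000 | 2 | 5.5% | 4.0% |
| 3000 / 3000, b = 0 | 2 | 3.9% | 0.0% |
| 3000 / 0, b = 1/3000 (plan's PTE of 0.5) | 1 | 98.9% | 84% |

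In the first row the ML time coefficient also rejects, in 98.6% of trials. By arithmetic, the EA coefficient goes from −2 − 3000/3000 = −3 to −2, a PTE of 0.33 (simulated median 0.34), while the interaction stays at −2, a PTE of 0. A fitted random-intercept mixed model on 60 simulated data sets agrees: EA time coefficient −2.97 to −1.97 (PTE 0.34), interaction −1.93 to −1.95 (PTE −0.01).

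**4. Glx.** From the plan: EA 1.5, ML 1.0, SD 0.6. Assumed: slope b = 1 per AIU, direct EA–ML effect d, and no other change in pain over time.

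- EA time coefficient: PTE = 1.5b / (1.5b + d).
- Interaction: PTE = 0.5b / (0.5b + d).
- d = 1.5: 1.5/3.0 = 0.50 against 0.5/2.0 = 0.25 (simulated 0.50 and 0.24).
- d = 1.0: 1.5/2.5 = 0.60 against 0.5/1.5 = 0.33 (simulated 0.61 and 0.33).

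In the d = 1.0 case the ML arm's own time coefficient also tests as mediated, in 93% of trials.

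**The case against.** The strongest reply is that the sentence gives one definition. Treatment-specific time slopes are a common verbal description of a treatment-by-time interaction, and the parenthesis may only name it. The text then speaks of a single coefficient and a single treatment effect, whereas arm-specific coefficients would give two PTEs and no rule for choosing between them. The power inputs and the interest in the interaction for connectivity point the same way. This stands as evidence of intent. It does not settle the wording: the within-arm quantity is named first, the interaction is joined to it by an or, and Aim 2 uses within-arm analyses elsewhere, such as the paired test in the 40 EA patients.

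It also stands that the false result is conditional. It needs the within-arm option, a non-zero mean biomarker change and a relation to pain; without either of the last two, rejection stays near 5% or below. For connectivity the plan expects mock laser to produce no reduction, and if so the two options give the same PTE (last row of the table). The separate EA–ML tests of each biomarker would also show an equal change beside the PTE, although they are not a formal precondition for a mediation claim. The logistic models for 50% and 30% pain reduction have one response per patient and no time term, so their treatment coefficient is naturally between arms. Finally, the Aim 2 hypotheses in Section 5 do not mention mediation; it appears in the synopsis and in Section 11.

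**Conclusion.** The estimand is ambiguous, and one of its two stated options is invalid for a claim about mediation of the EA–ML effect. Under that option, an equal 3000-voxel change in both arms is declared a mediator in about 98% to 99% of trials instead of about 5%. For Glx the PTE is roughly doubled. The rejection rates rest on the plan's voxel scale and b = 1/3000, with the direct effect on pain assumed; the Glx figures rest on an assumed slope and direct effect that the documents do not give.

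Three stronger readings are tempting and are not supported. A reader might infer that the plan has committed itself to the within-arm coefficient; the interaction is named in the same sentence, and the power calculation fits only the between-arm effect. A reader might infer that any biomarker that drifts with time will pass; one unrelated to pain does not. A reader might infer a threefold overstatement from the Glx figures; the mediated part is three times as large (1.5b against 0.5b), but on the PTE, the plan's own measure, the difference is about twofold.

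This should be fixed, but it does not undermine the design or the stated power.

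**What to change.** In the Mediation Analysis paragraph, delete the arm-specific time coefficient as an option. State that in the linear mixed mediation models for Hypotheses 1 to 3 the PTE and the Wald test use only the EA–ML treatment-by-time interaction, and that in the 50% and 30% logistic models they use the between-arm treatment coefficient.

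The cost is one or two sentences. No data collection or sample size changes, and the 81% power stands because it was already computed for the between-arm effect. The downside is that mediated effects may look smaller than within-arm figures would.

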2. SYNOPSIS

Study Title	Neuroimaging Approaches to Deconstructing Acupuncture for Chronic Pain
Study Sponsor	National Institutes of Health, National Center for Complementary and Alternative Medicine Grant Number: R01AT007550
Study Objective	To evaluate the impact of acupuncture-induced somatosensory afference on altered neurobiology and analgesia in FM.
Study Design	This study design has two components: 1) a cross sectional assessment of brain chemistry, connectivity and response to pain in healthy controls and age- and sex-matched fibromyalgia patients, and 2) a longitudinal assessment of the same fibromyalgia patients randomized to either electro-acupuncture (EA) or mock laser acupuncture (ML).
Study Interventions	Electro acupuncture and mock laser acupuncture. Treatments will be delivered at 2x/week for 4 weeks, for a total of 8 treatments.
Study Duration	The study duration for healthy controls will be 1 week, with a 4 week screening window. The study duration for fibromyalgia patients will be up to 10 weeks: 4- week screening window prior to baseline; 1-week of baseline, 4 week treatment period, and 1 week of follow up.
Sample Size and Population	We will evaluate 40 healthy controls and 80 fibromyalgia patients (n=40 EA and n=40 ML). Demographics will be representative of the population of southeastern Michigan.

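### The responder PTE compares logistic coefficients that sit on different scales, so it is biased even when treatment does not move the biomarker

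*Combined protocol and SAP*

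**What the plan says.** Section 11.2, under Aim 2, Hypothesis 1, defines the mediation measure in this way: "proportion of treatment effect explained by the biomarker (PTE) representing a relative change in the regression coefficient when biomarker is included in the model". The standard error comes from the bootstrap, "a two-sided 95% interval for the effect will be constructed", and a "Wald test with the statistic of the form (change in regression coefficient)/(bootstrap SE) will be used to test for the mediation effect". This is set out for a linear mixed model of BPI pain. One further sentence carries it to binary outcomes, with cut-offs at 50% and 30%: "Similar analyses will be done using a logistic regression model with clinically relevant reduction in pain".

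The power statement covers the linear case only: "Power analysis targets biomarkers with the mediation effect of PTE=0.5", with a Sobel test giving 81%. Hypotheses 2 and 3 say that mediation for Glx, GABA and evoked-pain activation follows the connectivity method, so they inherit the logistic version. Section 11 contains no correction for rescaling of logistic coefficients and no probability-scale indirect effect.

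**The concern.** In a linear model, adding a variable that treatment does not affect leaves the expected treatment coefficient unchanged, so a drop in the coefficient can be read as mediation. This does not carry over to logistic regression. If treatment has an effect and the added variable predicts response within arm, the conditional log-odds ratio is larger in size than the marginal one, even in a perfectly randomised trial. The difference between the two coefficients then reflects both mediation and the change of scale. Bootstrapping gives a standard error for that mixture but does not separate its parts.

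Three results are at stake:

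- One dataset could show a linear PTE near 0.5 and a responder PTE near 0.25, and the gap could be read as biology.
- A biomarker that treatment does not touch could appear to suppress the treatment effect.
- Because the rescaling depends on how strongly each biomarker predicts pain, responder PTEs for connectivity, Glx, GABA and evoked activation would not be comparable. The distortion is largest for the strongly correlated biomarkers the trial hopes to find.

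**Working it through.** **Inputs (Section 11.2).** Treatment effect on connectivity a = 3000 voxels; total effect on pain change 2; target PTE 0.5; SD of treatment variable 0.5; SD of connectivity change 4500; residual SD of the full pain model 1.5; stated squared correlation of treatment and biomarker 3.7e-05; n = 80 (Synopsis, 40 per arm). It follows that b = 0.5 × 2 / 3000 = 1/3000 per voxel and the direct effect is 1.

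**The plan's own figure.** Sobel z = a·b·√n / √[a²·1.5²/(4500²(1−r²)) + b²·4500²(1−r²)/0.5²] = 1 × 8.944 / √(1.0 + 9.0) = 2.83. Power is Φ(2.83 − 1.96) = 80.7%, which agrees with the stated 81%. The linear calculation reproduces on its inputs.

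**Implied strength of the biomarker.** Per SD of 4500 voxels the slope is 4500/3000 = 1.5. The within-arm correlation with pain change is 1.5/√(1.5² + 1.5²) = 0.71. The plan separately expects at least 0.5 in the EA arm. The slope for r = 0.5 is 1.5 × 0.5/√0.75 = 0.87.

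**Hand approximation.** Cut a normally distributed pain improvement at a threshold and use probit coefficients. The coefficient without the biomarker is the total effect divided by the marginal within-arm SD. The coefficient with it is the direct effect divided by 1.5. Hence

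PTE(binary) ≈ 1 − (direct/total) / √(1 − r²).

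- Target, direct/total = 0.5, r² = 0.5: 1 − 0.5/0.707 = 0.29, where the linear PTE is 0.50.
- Treatment does not move the biomarker, direct/total = 1, r² = 0.5: 1 − 1/0.707 = −0.41, where the linear PTE is 0.
- The same with r = 0.5: 1 − 1/0.866 = −0.15.

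**Large-sample logistic fits.** Data were simulated from the same linear model, 2,000,000 patients per setting, with the threshold set to give the mock laser (ML) response rate shown. These rates are assumptions. The percentage-reduction responder is represented by a cut on improvement.

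| Setting | Linear PTE | Logistic PTE at ML 10% / 20% / 30% |
|---|---|---|
| Plan's target | 0.50 | 0.29 / 0.26 / 0.25 |
| a = 0, plan's slope (r = 0.71) | 0 | −0.43 / −0.49 / −0.51 |
| a = 0, r = 0.5 | 0 | −0.16 / −0.19 / −0.19 |
| a = 0, r = 0.3 | 0 | −0.05 / −0.06 / −0.06 |
| a = 0, r = 0.18 | 0 | −0.02 / −0.02 / −0.02 |
| Biomarker moved, b = 0 | 0 | 0.00 / 0.00 / 0.00 |

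As an example, with a = 0, the plan's slope and 20% ML response, the treatment log-odds ratio goes from 1.542 to 2.293 when the biomarker is added: 1 − 2.293/1.542 = −0.49. Reading 4500 as the total rather than the within-arm SD changes the target row to 0.30 / 0.28 / 0.27. Over ML rates of 5% to 50%, the a = 0 figure at the plan's slope runs from −0.36 to −0.51 (to −0.55 with logistic errors). Full mediation still reads as about 1.

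**The planned test at n = 80.** I ran 400 simulated trials per setting with 200 bootstrap resamples each, using a robust bootstrap SE and a very small ridge penalty against separation.

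- With a = 0 and the plan's slope, the Wald test rejected in 24.5% (ML 20%) and 28% (ML 30%) of trials against a nominal 5%, always in the negative direction. About 98% of PTE estimates were negative.
- At the plan's target (ML 30%), the median PTE was 0.23 and the test rejected in 16.5% of trials. Part of this loss against 81% comes from dichotomising, not from rescaling.
- With b = 0, it rejected in under 1% of trials and the median PTE was 0.01.

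**The case against.** The strongest reply concerns scope.

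- The mediation method is specified and powered for the linear model. The responder version is one sentence with no power figure or decision rule.
- The distortion needs both a treatment effect and a biomarker that predicts response within arm. It vanishes when b = 0, the other way of having no mediation.
- The largest figures use the within-arm correlation of 0.71 implied by the Sobel inputs. At the hypothesised 0.5 they fall by more than half, and near the interim cut-off of 0.18 they are negligible.
- The plan expects the correlation in EA but not in ML. With r = 0.5 in EA, 0 in ML and a = 0, the logistic PTE is only about −0.04 to −0.07.
- The bias runs toward zero or negative values, so it does not manufacture positive mediation.
- A linear share of 0.50 is not automatically the right share on a binary scale. A standardised risk-difference analysis of the same data gives 0.40 to 0.60, depending on the response rate and on which indirect effect is taken.

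All of these stand as limits on size and reach. None removes the fault. The common slope is the one in the plan's own PTE and Sobel model, and a logistic PTE of 0.25 to 0.29 lies below even the 0.40 to 0.60 range. In the no-mediation setting the standardised indirect effect is about 0, whereas the logistic PTE is not.

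**Conclusion.** The concern holds for the 50% and 30% responder mediation analyses. At the plan's target the logistic PTE is roughly half the linear share (0.25 to 0.29 against 0.50). When treatment does not affect the biomarker it is −0.43 to −0.51 at the plan's slope and −0.16 to −0.19 at r = 0.5, instead of 0. It is close to 0 for weakly correlated biomarkers and small if the correlation exists only under EA.

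The figures rest on assumed ML response rates of 10% to 30%, which matter little, and, apart from the EA-only case, on a common biomarker slope in both arms. The linear PTE and the Sobel power are not affected. The likely harm is missed mediation or apparent suppression, plus a spurious conflict with the linear analysis. This should be corrected, but it does not threaten the trial's main mechanistic analyses.

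**What to change.** In Section 11.2, confine the coefficient-difference PTE and its Wald test to the linear model. For the 50% and 30% responders, fit a mediator model (biomarker change on treatment) and an outcome model (response on treatment and biomarker). Allow a treatment-by-biomarker interaction in the outcome model, since the plan expects the association in EA and not in ML. Standardise the predicted probabilities to obtain direct and indirect effects as risk differences, with bootstrap intervals.

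The text should name which indirect effect is reported. One choice is the change in response probability when the biomarker moves from its ML to its EA distribution with treatment held at EA, paired with the direct effect that makes the two sum to the total. It should also warn that this share need not equal the linear PTE, and apply the same wording to Glx, GABA and evoked activation.

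The cost is revised analysis-plan wording and a little code. No new data, visits or patients are needed.
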